The flowchart of the study is presented in Figure 1. Randomization was carried out among the 23 priority districts in this study with a ratio of 2:1 (that is, 2 intervention districts per 1 control district). The details of randomization are explained in section B.4 of this document. **The assigned 15 intervention districts and 8 comparison districts** are described in Table 6. Potential participants in the intervention area will be screened through the inclusion and exclusion criteria established for

this study. The criteria for participants who are eligible for this study are explained in section B.3 of this document and Annex2.

According to the Indonesian Ministry of Health's current recommendation, HIV blood test at an authorized health facility is still the current practice for HIV diagnosis. Both participants in the intervention and comparison area will be offered for HIV blood test at a health facility. Participants in comparison areas and participants in intervention areas who agree to take HIV test at a health facility will then be managed further according to the existing guideline or "standard of care." For participants in intervention areas who refuses to have her blood drawn for HIV test at a health facility will then be offered self-testing using OraQuick®. Participants will then fill and sign the informed consent to participate in CBS study.

Next, participants will be offered to do the test assisted or unassisted. If the participant chooses to perform the test assisted, the PL/PE will help her from filling in a baseline survey, performing the test, and filling in a post-test survey. If the participant chooses to perform the test unassisted, there will be two options for the participant to get the test kit. First, PL/PE will deliver the test kit for the participant, help with filling in the baseline survey on the spot and give information about uploading test results and the post-test survey, along with a hotline number to call for any questions and concerns, including follow-up steps after participants have received the results. The second method, participants will be given a link online which will entitle information of this study, eligibility criteria, informed consent, baseline survey, link to order a test kit, link to upload result and link to fill in the post-test survey. Participant who chooses this second method will also be given hotline number should there be any further inquiries.

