3.1 Study kick-off										
3.2 Data collection										
4. Data analysis and report writing										
5. Workshop for study finding dissemination										

3. Eligibility Criteria

The target audience for the intervention to be evaluated are FSW in Intervention districts that meet the criteria outlined below.

Inclusion criteria

- Women, 18 years or older at enrolment
- Reports transactional sex (vaginal, oral and/or anal) at least once in the past month
- No HIV test in last 6 months
- Self-reported HIV negative OR HIV status unknown

Exclusion criteria

- Unwilling to participate for any reason
- Concurrently participating in another HIV prevention study

4. Randomization

Stratified randomization was carried out for the 23 priority districts involved in this study. First, sampling strata were created by sorting the mean average value of achieved HIV testing target per semester from 2018-2019 in each district from the largest to the smallest. The second step was to sort the districts into eight groups of three districts, except for the last group which will only consist of two districts. Randomization for intervention and comparison group were then carried out within these groups of eight with 2:1 ratio (2 intervention: 1 comparison).² The results of stratified randomization are presented in Table 6. In separate table, Table 7 contains 15 intervention districts and Table 8 contains 8 comparison districts.

² A 2-to-1 intervention to comparison district ratio was chosen in order to increase the likelihood of recruiting a sufficient number of FSW for community screening to reach the sample size target considering the relatively short time frame available for for study implementation.

Table 6. Allocated intervention group and comparison group

No	Kab/Kota	Region	Achieved target of HIV testing per semester (2018-2019)	Group
1	Kota Denpasar	3	982	Intervention
2	Kota Makassar	3	866	Comparison
3	Kota Palembang	1	694	Intervention
4	Kota Jakarta Utara	1	612	Comparison
5	Kota Medan	1	575	Intervention
6	Kota Surabaya	3	568	Intervention
7	Kota Jakarta Barat	1	544	Intervention
8	Kota Bandung	2	487	Comparison
9	Kota Jakarta Timur	1	479	Intervention
10	Kota Jakarta Pusat	1	473	Intervention
11	Kota Jakarta Selatan	1	448	Comparison
12	Kota Sorong	4	415	Intervention
13	Kab. Tangerang	1	391	Intervention
14	Kota Bogor	2	374	Intervention
15	Kota Jayapura	4	323	Comparison
16	Kota Bandar Lampung	1	319	Comparison
17	Kota Depok	2	287	Intervention

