Sample size requirements for the third question measurement pertains to the number of FSW who test positive for HIV at a health facility and are thus eligible to initiate treatment. This will depend upon (1) the number of FSW presenting at health facilities for testing and (2) the positivity rate among those tested. Sample sizes should thus be calculated accordingly. If we assume a testing positivity rate of 3%, it is apparent that the expected number of FSWs who would be eligible for treatment will be small and we will lack sufficient statistical power to make meaningful comparisons with comparison districts. For this reason, it is recommended that the impact of community screening among FSW be measured using SIHA data for FSW in both intervention and comparison districts. This estimate of impact derived in this way will be confounded if it were to be the case that interventions other than HIV self-testing were to be better implemented in intervention vs. comparison districts. It might be possible to minimize this potential bias by including measures of intervention implementation performance in the intervention and comparison districts in multivariable analyses. Thus, a large enough sample size is required to ensure sufficient power to determine the difference in the intervention and control districts.

C. THE INTERVENTION

1. General Description of The Intervention

FSW who meet the eligibility criteria will be offered for HIV blood test first. Participants who wish to take the test will then managed according to the current guideline for standard of care. Participants who disagree to take HIV blood test will then be offered screening test with Ora-Quick®. There will be with two options for community HIV screening by Peer Leaders: (1) in a convenient community setting assisted by PL/PE (assisted screening) or (2) in a setting of their own choosing without assistance from PL/PE (unassisted screening). FSW will also be able to access a community-based screening test by following online link from messages spread through WhatsApp number without having to come into contact with outreach workers. The saliva-based Ora-Quick® test kit will be used for community screening.

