
3. Implementation Guidelines: Unassisted Community Screening

Because of differences in the structure of sex work and in the enabling environment in different districts, it will be necessary to develop the details of unassisted community screening on a district-by-district basis. Ideally, the same unassisted community screening intervention would be implemented in the same way in all intervention districts, but if this is not possible due to the factors outlined above, allowing some details to vary across districts is preferable to trying to implement a standard protocol that is expected a priori to fail in some locations.

For unassisted community screening, in which OW don't have face-to-face contact with FSWs, possible mechanisms for distributing Ora-Quick test kits entail:

- a. Trained PE/PL identifying various online networks in which FSWs use to solicit their service.
- b. Trained PE/PL building trust from FSWs to participate in the study.
- c. Trained PE/PL send broadcast message containing brief information of the study, eligibility criteria for participation, step-by-step method to order the kit and have it delivered to their address, short link for description of how to use the kit (flier or short video), and mandatory baseline and post-test survey. Test kit delivery will be done by same-day delivery system (Go-Send/Grab Send) from selected places where the test kit will be stored (Implementing Unit Office or selected health care facilities) to client's address. Trained peer leader/peer educator could also distribute the test kit but not participating in the testing by assisting FSW during the test.

- d. Trained PE/PL carrying out follow-up for FSWs being previously approached for the test. The same trained PE/PL is assigned to be the contact person/hotline for each FSW they approached and agreed to take the test.
- e. FSW send/upload results of the test along with a completed post-test survey. Cash (mobile top-up) incentive will be transferred to FSW who send the test results and post-test survey. Every kit distributed will have unique code and FSW will be asked to fill it in both baseline and post-test survey to ensure one FSW is entitled to only one test kit.

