4. Numbering System for Test Kit and Other Instruments

a) Recording Test Kit ID

Every test kit will have a unique ID number, which will later be referred to as the Kit ID number. The Kit ID Number is to be filled in on all instruments and forms that are to be linked to the test results (e.g., baseline survey, test results form, post-test survey, routine data record in each IU, etc.). This number needs to be identified at all times to make sure that each participant is only assigned to one test kit, matching the kit with the results, and to track the stock of the test kit remained. The format of this ID kit will be “01-001”, where the first 2 digits are to identify the number of the district in which participants take the test, and the last 3 digits are to identify which test kit the participant is using. This test kit ID will also be later used for each IU to track the distribution of the test kit. Every test kit being distributed, either in a fixed place or delivered through same-day delivery services, will be recorded and tracked by each IU. An MS Excel or MS Access form will be developed to record and track the Kit ID Number.

b) Recording temporary FSW ID

On the ground of confidentiality, participants' full name will not be revealed and used within this study. A new system to ensure the reliable yet confidential identification of study participants needs to be established. Every participant in the study will be assigned to a temporary FSW ID. The format will be **the first 4 letters of participants' names added by the date of birth (yy/mm/dd)**. For example, a participant named “INDRIYANTI” who was born on March 5th 1976, her temporary FSW ID will be “INDR760305”. For FSW whose name contains only 3 letters, the number zero will be added after the last letter. For example, an FSW whose name is “AYU” and was born on March 5th 1976, her temporary will be “AYU0760305”. This temporary FSW ID will be used to ensure that each participant is only assigned to one test kit, to track test results, and to be filled in the baseline and post-test survey.

c) Matching Test Kit ID and temporary FSW ID

To match the test kit ID and temporary FSW ID, an automatic system needs to be developed to detect it precisely. This way, we can be sure that each participant only gets to participate in this study once (from receiving the kit, performing the test, and reporting the result).

d) Paper Based Data Collection

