Annex 1. Flowchart of Routine Data Recording

Annex 2. Eligibility Form

Eligibility Participants Form for Intervention

To be completed by PL/PE during FSW outreach

These checklists are to be completed by PL/PE during FSW outreach to assess the eligibility of FSW to participate in this study. If questions number 1-7 is answered “Yes”, then participant is eligible for the study. If question number 8 is answered “Yes”, then participant is not eligible for the study, but eligible for “blood test study in health facility”.

No	Criteria inclusion	Yes	No
1	Female, aged 18 years old or more		
2	Admit having transactional sex (vaginal, oral, or anal) at least once within the last one month		
3	Have never had any HIV test taken within the last 6 months		
4	Self-reported HIV Negative OR HIV status unknown		
5	Agreed to participate in this study		
6	Not currently participating in any other HIV prevention study		
7	After being offered for HIV testing in health facility, participant stated: A. Agree for HIV testing in health facility* B. Not agree for HIV testing in health facility**		

Note:

* Use information form for VCT

** Use information form for OFT

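### No described step keeps online kit orders inside the intervention districts, and no rule says which arm an out-of-district self-tester belongs to

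*Combined protocol and SAP*

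**What the plan says.** The intended population is clear in B.3: "The target audience for the intervention to be evaluated are FSW in Intervention districts that meet the criteria outlined below". B.1 and C.1 likewise describe screening as something added in intervention districts only. The operating parts of the plan do not carry that limit through:

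- **Access (C.1).** "FSW will also be able to access a community-based screening test by following online link from messages spread through WhatsApp number", and this "without having to come into contact with outreach workers".
- **Online link (B.1).** It bundles study information, eligibility, consent and baseline survey with a "link to order a test kit, link to upload result and link to fill in the post-test survey". No district check is listed.
- **Delivery (C.3).** The broadcast gives a "step-by-step method to order the kit and have it delivered to their address". "Test kit delivery will be done by same-day delivery system (Go-Send/Grab Send) from selected places where the test kit will be stored", namely an implementing unit's office or a chosen facility. No delivery boundary is stated.
- **Dispatch condition (section H).** The only one stated for the online route is a ticked consent box.
- **Eligibility (B.3, Annex 2).** The criteria and checklist cover age, sex work, last test, known status, willingness, response to the facility offer, and "Not currently participating in any other HIV prevention study". None concerns district.
- **Baseline questionnaires (Annexes 4 and 6).** They ask the type of venue where clients are found, not the district of work or residence.
- **Kit code (E.4).** "the first 2 digits are to identify the number of the district in which participants take the test". How those digits are assigned is not said.
- **Recording and analysis (E.3, F).** The self-test rows of the recording table are marked as not collected for the control group. Section F groups assisted and unassisted users as intervention and gives no rule tying a woman to her own district.

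**The concern.** A cluster-randomised comparison needs each woman to be exposed, and counted, according to the district she belongs to. Here a woman in a comparison district who receives a forwarded link can meet every listed criterion and order a kit, and nothing described would stop or identify her. She has some reason to order: section C.5 pays 50,000 IDR for the baseline survey, 100,000 for uploading a result and 50,000 for the post-test survey, 200,000 IDR in all.

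Two distortions are possible, in opposite directions. If she then tests at a facility and is counted under her own district, the comparison rate rises and the effect is diluted. If her self-test is counted as intervention, which is the only place the recording table has for it, she can inflate the intervention rate. That matters for the section F comparison in which self-tests count as tests received. One woman should not be assumed to do both within one endpoint, and the plan does not settle which would apply.

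**Working it through.** **1. Where leakage is plausible.** Randomisation was stratified by testing volume, not geography (B.4). In Table 6, Jakarta Barat, Pusat and Timur are intervention; Jakarta Utara and Selatan are comparison. Outreach per year in the eight comparison districts (Table 5) is

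1,933 + 3,129 + 2,905 + 879 + 1,317 + 2,164 + 2,683 + 983 = 15,993.

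Utara and Selatan contribute 3,129 + 2,905 = 6,034, and 6,034 / 15,993 = 0.377 (38%). By tests per semester (Table 6) their share is (612 + 448) / 3,342 = 1,060 / 3,342 = 32%.

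**2. The plan's own sample size.** With P1 = 0.5, P2 = 0.6, mean proportion 0.55 and 90% power, the two-proportion formula gives 423 per group at one-sided 5%. Then 423 × 1.5 = 634.5, or 635, and 634.5 × 1.2 = 761.4, or 761. So the stated figures reproduce at one-sided 5% with multiplier 1.5. They also reproduce with Z = 1.96 and multiplier √1.5 (518.2 × 1.2247 = 634.6). Z = 1.96 with multiplier 1.5, as printed, gives 777. Because the plan does not settle the test, both are shown below. None of these includes an allowance for contamination.

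**3. Illustrative dilution.** Assumptions, none from the documents: a share c of women in Utara and Selatan obtain kits; each such woman reaches the intervention rate of 0.6; all are counted in the comparison arm; weights follow outreach. Then

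P1(c) = 0.5 + 0.10 × 0.377 × c, and effect = 0.10 × (1 − 0.377c).

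Power uses n = 635 / 1.5 = 423.3 effective women per group:

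z = [√423.3 × (0.6 − P1) − z_α × √(2P(1 − P))] / √(P1(1 − P1) + 0.24), with P the mean of P1 and 0.6.

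For c = 0 at one-sided 5%: (20.575 × 0.10 − 1.645 × 0.7036) / 0.70 = 1.286, so power is 90%.

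| c | Effect (points) | Power, one-sided 5% | Power, two-sided 5% |
|---|---|---|---|
| 0 | 10.0 | 90% (z = 1.286) | 83% (z = 0.969) |
| 10% | 9.6 | 88% (z = 1.176) | 80% (z = 0.859) |
| 30% | 8.9 | 83% (z = 0.956) | 74% (z = 0.639) |

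The two-sided column keeps the multiplier at 1.5, which is why it starts below 90%. Weighting by tests instead (0.317) gives effects of 10 × (1 − 0.0317) = 9.7 and 10 × (1 − 0.0951) = 9.0 points.

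**4. Inflation.** The documents give nothing from which to size the opposite bias, so no figure is offered. The table covers dilution only.

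**The case against.** The strongest reply is that the order page is not reproduced, the website and forms were still to be developed, and C.3 leaves unassisted details to each district, so a district question may exist. The consent form, Figure 1 and Annex 1 were not available for this check. A delivery address must be collected, each implementing unit logs every kit (E.4), and the Annex 9 referral card carries an address next to the kit code. District could therefore be recovered for courier orders. Annex 2 is headed as a form for the intervention and is filled in during outreach.

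Much of this stands. It limits the point to what is described: no form shown asks district, and no use of the address is specified. It does not close the gap. Annex 2's outreach setting does not cover women who order without meeting an outreach worker, the referral card comes into play after a kit has been released, and no attribution rule exists even if the address is known.

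A reader might infer that the kit code guarantees miscounting. The documents do not support that. E.4 does not present the code as a guard against leakage. Read literally, a comparison-district woman testing at home would carry a comparison-district number and be flagged. She would be missed if kits are pre-numbered from an intervention unit's stock or if she tests across a boundary. A reader might also infer that unmatched numerators are certain; E.3 does count online visitors, eligible women and baseline completions, so some denominator exists, though not by district.

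**Conclusion.** The gap is real and should be closed. The plan as written allows a comparison-district woman to enrol online and does not say how she would be counted. The risk is most plausible across Jakarta's three-to-two split, where the exposed districts hold 38% of comparison-district outreach.

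The direction of bias is not determined. The dilution figures (10 points falling to 9.6–8.9; power 90% to 88–83% one-sided, or about 83% to 80–74% two-sided) rest on an assumed leakage rate and on the generous assumption that every leaked kit gives the full 10-point gain in facility testing. They show a modest loss, not a failed design. A reader might extend the leakage to all comparison districts and find a much larger loss. The documents do not support that: Makassar, Jayapura and Bandar Lampung share no province with an intervention district.

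**What to change.** - Add one required item, district, with a single pre-specified definition (main place of work or residence), to Annex 2, the online form and Annexes 4 and 6.
- Check the delivery address before dispatch and ship only within the 15 intervention districts.
- State in section F that every woman is analysed under her own district as randomised, not under the kit's district digits, and say in E.4 how those digits are assigned.
- Report the number of orders received from outside the intervention districts, by district.

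The cost is one form item, an address check at ordering and a few sentences in the plan. The downside is that a few online requests will be declined.
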